coordinator will follow on this process to ensure that the patients perform these interim studies. Development of hypothyroidism will be assessed using these tests at 4, 6 and 8 weeks using the cutoffs for free thyroxine and TSH values as described previously³. For the 8 weeks visit all patients will be asked to bring their medication bottles and the study coordinator will perform a pill count to assess compliance with the protocol. Final evaluation for both groups will be at 6 months after RAI at which time patients will undergo a phone questionnaire which will assess the rate of recurrence of hyperthyroidism and test the feasibility of screening for changes in GO status over the phone. In both groups a quality of life instrument will be used at baseline, 4, 6 and 8 weeks and at 6 months. We will use the hypothyroid-Health Related Quality of Life (hypothyroid-HRQL)⁷ and also the Thyroid Specific Questionnaire (TSQ)⁸. These questionnaires are disease-specific for hypothyroidism. A major advantage to our study is also their ability to be self-administered. These last 2 interventions will be used to assess the feasibility of using them in the larger, multi-center trial where GO prevention and QOL benefit will be the primary outcomes.

[figure not shown]

Figure 3 – Trial flow chart

b. Study Subjects - Inclusion criteria target all adult patients (ages 18-70 years) with GD who will receive RAI for treatment of GD. We plan to have 60 individuals complete the study. For that up to 90 individuals may need to be screened. Exclusion criteria - Patient with clinically manifest GO will be excluded from the study. We will also exclude patients with recent (<1 yr.) history of arrhythmias or any history of ventricular arrhythmias, those with preexistent cardiomyopathy, those with malnutrition and those with psychiatric history that could get worse if patient remains persistently hyperthyroid. Patients unlikely to return for the planned follow-up visits, to comply with the blood drawing schedule and with the completion of the hypothyroid-HDQL and TQS questionnaires will also be excluded. If a medical examination was performed within the last 4 weeks by an endocrinologist we can discuss the study over the phone. The consent material can be exchanged by mail or fax.

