The sample size for this study is based on the incidence of hypothyroidism primary endpoint using an $\alpha=0.10$ (two-sided), $\beta=0.10$. The proportions of participants that develop hypothyroidism in the placebo and experimental groups are assumed to be 60% and 20%, respectively. A sample size of 30 per group will provide 90% power to detect a difference between the group proportions of 40% using the two-sided Fisher's Exact test.

Primary Endpoint Analysis:

The difference in the incidence rates of hypothyroidism at 8 weeks will be tested using Fisher's exact test.

Exploratory Endpoint Analysis:

Change in quality of life is measured serial over the course of the study follow-up. Change from baseline will be assessed using a hierarchical linear model ("growth curve"). The primary parameter of interest from the model will be the treatment by time interaction term. Time, for this study, will be a collection of indicator variables representing each assessment point. The incidence of GO will be tested using Fisher's exact test.

Safety Analysis:

Frequency tables of adverse events by treatment groups at the patient level will be tabulated. The relative risk of developing a serious, and at least potentially related, adverse event will be estimated along with the 90% confidence interval for relative risk.

Additional Statistical Considerations

The primary analysis will be conducted according to the intention to treat principle. Efforts will be made to ascertain the incidence of hypothyroidism even in participants that are lost to follow up. In the event the data cannot be obtained, the primary analysis will assume these participants are positive for hypothyroidism. Sensitivity analysis will be conducted on the per protocol data set.

Missing data for the primary endpoint is addressed through the intention to treat analysis. Missing data in exploratory endpoints could occur. The analysis plan for the QOL endpoint include maximum likelihood estimation that allows for missing data, provided the data are missing at least missing at random.

A P-value < 0.10 will be considered significant for the primary endpoint and exploratory analyses.

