i. Strengths - The design for this study was developed based upon the findings of our retrospective cohort study described above. This trial design will compare an active intervention with the current practice using the benefit of blinding and randomization for eliminating a placebo effect and differences in known and unknown confounders between the groups. It is also minimally disruptive of patients schedule while providing potential benefit for both quality of life and decreasing the risk of GO. By having the free thyroxine values at 0, 4, 6 and 8 weeks it will provide us with the ability to better predict the development of euthyroidism/hypothyroidism, to decide on the best levothyroxine dose and to adjust the therapeutic sequence accordingly. We have allowed for a low recruiting percentage to avoid the possibility of extending the study beyond the planned funded time frame.

j. Limitations - There may be patients that will report increase/recurrence of hyperthyroidism-like symptoms. Those cases are rare and in the literature early T4 therapy (started at 50 mcg daily 2 weeks after RAI) required discontinuation due to symptoms of thyrotoxicosis in only 7/314 patients (2.2%)^{1,4}. In that case we will decrease the dose of levothyroxine x 2 weeks and if the symptoms persist the medication will be discontinued. Beta-blockers will be used liberally at the discretion of the treating physician.

k. Regulatory aspects – We have discussed extensively and consulted with the Office of Research Regulatory Support on the issue of applicability for an IND application. The intention of the study is to treat with levothyroxine patients that are in the very early stages of developing hypothyroidism. The timing of the therapy is based on data that documents onset of hypothyroidism well before the usual 8-12 weeks follow-up. We have proposed to start at a very conservative dose (25 mcg) which represents 25% of the median dose used in the therapy of hypothyroidism. This is quite safe as mentioned above, with only 2.2% of patients required discontinuation of therapy in similar studies in Europe. In addition the patients will be evaluated 4 weeks later and the dose adjusted as clinically indicated. Given all these considerations we have concluded that we are not outside of the scope of the FDA-approved indication for levothyroxine in hypothyroidism management and we have decided against submitting an IND application.

Table 3 – Schedule of Events

Schedule of Events					

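### The plan's one between-arm safety estimate, a relative risk for serious related adverse events, has no method for zero counts, and the named safety endpoint has no between-arm estimate

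*Combined protocol and SAP*

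**What the plan says.** Under Safety Analysis, section IV.h has two sentences. The first provides patient-level frequency tables of adverse events by arm. The second states that the "relative risk of developing a serious, and at least potentially related, adverse event will be estimated along with the 90% confidence interval". No interval method is named, and zero counts are not mentioned.

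The same section lists one safety endpoint, new or worsening symptoms of hyperthyroidism. No estimate, test or interval is attached to it beyond whatever the frequency tables show. The Fisher's exact test on ophthalmopathy is listed as exploratory, not as safety.

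The closing paragraph of section II gives the hypothesis in two parts: early levothyroxine prevents overt hypothyroidism, and it does so with no rise in symptomatic hyperthyroidism. That paragraph also says this study must be completed before the multicentre trial can be designed.

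On size, section IV.b says "We plan to have 60 individuals complete the study", and section IV.h says "A sample size of 30 per group will provide 90% power" for the primary endpoint. The nearest safety rate is in section IV.j: 7 of 314 patients in published cohorts stopped early levothyroxine because of thyrotoxic symptoms, and such cases are described as rare.

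**The concern.** A relative risk divides by the placebo proportion, so it has no finite value when the placebo arm has no events. When only the levothyroxine arm is empty, the relative risk is 0 and the usual interval, built on the log scale, cannot be computed. With 30 per arm and an uncommon event, both situations are likely enough to need a rule in advance. Without one, the choice of continuity correction, interval method or substitute measure is made after the counts are known.

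The second gap concerns which event is compared. The comparison is attached to serious related events, whereas the hypothesis and the named endpoint concern hyperthyroid symptoms. As written, the trial could finish with no usable comparison for the first and no planned one for the second, although its results are meant to inform the next trial.

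**Working it through.** **The plan's own figure.** Section IV.h uses two-sided alpha 0.10 and rates that "in the placebo and experimental groups are assumed to be 60% and 20%, respectively". Exact enumeration of the two-sided Fisher test gives 90.9% power at 30 per arm and 89.6% at 29. The stated 90% reproduces, and n = 30 per arm is taken as the base for the safety calculation.

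**Assumed event rate.** The documents give no rate for serious, at least potentially related events. I take 1% to 2.2% per arm as a working range. The upper value is 7/314 = 2.23% (section IV.j). It counts a different event (stopping for symptoms) under a different regimen (50 mcg daily from 2 weeks after radioiodine, against 25 mcg daily from about 4 weeks in section IV.a). A rate of 5% is added as a high-side check.

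**Formulas.** With true rates pA (active) and pP (placebo):
- placebo arm empty: (1 − pP)^30
- both arms empty: (1 − pA)^30 × (1 − pP)^30
- at least one arm empty: 1 − [1 − (1 − pA)^30] × [1 − (1 − pP)^30]

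For 2.23% in both arms, 0.9777^30 = 0.508. Both empty is 0.508² = 0.259, and at least one empty is one minus 0.492², which is 0.758.

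| Active / placebo rate | Placebo empty | At least one empty | Both empty |
|---|---|---|---|
| 2.2% / 2.2% | 50.8% | 75.8% | 25.9% |
| 2.2% / 1% | 74.0% | 87.2% | 37.6% |
| 1% / 1% | 74.0% | 93.2% | 54.7% |
| 5% / 5% | 21.5% | 38.3% | 4.6% |

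With equal rates, the chance of at least one empty arm drops below one half at about 4.0% per arm. The chance that the placebo arm is empty drops below one half at one minus 0.5^(1/30), which is 2.3%.

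**What the relative risk shows when it can be computed (90% intervals, log scale).**
- 0 v 0, with 0.5 added to each cell: estimate 1.0, interval 0.04 to 26;
- 1 v 0, with 0.5 added: estimate 3.0, interval 0.21 to 43;
- 1 v 1, no correction: estimate 1.0, interval 0.10 to 9.8;
- 2 v 1, no correction: estimate 2.0, interval 0.28 to 14.3.

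**What the risk difference shows (Newcombe 90% intervals, active minus placebo).**
- 0 v 0: −8.3 to +8.3 percentage points;
- 1 v 0: −5.3 to +13.6 points;
- 2 v 0: −2.7 to +18.3 points.

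The exact one-sided 95% upper bound for one arm at 0/30 is one minus 0.05^(1/30), which is 9.5%.

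**The case against.** A reader might infer from the 76% to 93% that the relative risk will most likely not exist. That goes too far. Those figures are for either arm being empty. The relative risk lacks a finite value only when the placebo arm is empty, which at 2.2% is 51%, about an even chance. Nor does the plan commit to a log-scale interval. A score interval for the relative risk still gives a one-sided bound when one arm is empty: at 30 per arm the 90% lower bound is about 0.38 for 1 v 0, and the upper bound is about 2.6 for 0 v 1. With that method, only 0 v 0 defeats the analysis.

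It is also tempting to treat 2.2% as a ceiling because stopping for symptoms sounds broader than a serious related event. The documents do not establish this: a serious related event need not be thyrotoxic or lead to stopping, so neither set contains the other. The rate remains an assumption.

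Nor does the safety part of the hypothesis rest on this relative risk. It concerns hyperthyroid symptoms, and a perfectly estimated relative risk for serious events would not answer it.

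Finally, the frequency tables will let any reader derive a difference, and no margin, stopping rule or go/no-go decision in the documents uses the relative risk.

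All of this stands as a limit on the claim. It does not remove the gap: the plan promises an estimate and interval, names no method that copes with zeros, and sets no comparison for its own safety endpoint. Counts in a table are neither an estimate nor a statement of uncertainty.

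**Conclusion.** The point holds in a limited form. The planned safety comparison has no zero-count method. At assumed rates of 1% to 2.2% per arm, there is a 51% to 74% chance of no finite relative risk, a 76% to 93% chance that the usual log-scale interval fails, and a 26% to 55% chance that both arms are empty and no relative-risk method yields anything. These figures depend on the assumed rate and on 30 per arm; at 5% per arm the chance of any empty arm is 38%.

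The absence of a between-arm estimate for new or worse hyperthyroid symptoms depends on no assumed rate; it follows from reading sections II and IV.h together. The primary endpoint and its power are unaffected. The change should be made because the measure chosen is poorly suited to sparse counts and the safety question actually posed has no planned estimate.

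**What to change.** In section IV.h, Safety Analysis:
- Replace the relative risk with the risk difference, active minus placebo, and a 90% interval by a named method valid with zero cells (Newcombe or Miettinen-Nurminen).
- Report each arm's exact one-sided 95% upper bound.
- Apply the same risk difference and interval to the proportion of patients with new or worse hyperthyroid symptoms.

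This takes a few sentences and changes neither the sample size nor the primary analysis. The small downside is candour: the intervals will be wide, ±8.3 points even with no events in either arm, and will show how little 30 per arm can exclude.
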